2.2.1.3. E-602 Toxicology

The toxicity of E-602 IV infusion was evaluated in male and female cynomolgus monkeys in a toxicology and toxicokinetic study. E-602 was administered at doses of 5 to 200 mg/kg as a single dose at 5 or 30 mg/kg, weekly at 100 or 200 mg/kg, or twice weekly at 100 mg/kg. All infusions were given in 30 minutes.

E-602 at all doses was well tolerated and resulted in only minimal changes in liver enzymes (minimal increases in ALT and AST and minimal decreases in ALP and gamma-glutamyl transferase (GGT) in animals administered ≥100 mg/kg), which were generally within the normal range of levels for cynomolgus monkeys at the test facility and considered of uncertain relationship to E-602 administration and non-adverse. The no-observed-adverse-effect level (NOAEL) was considered 100 mg/kg for weekly dosing.

Please refer to the current E-602 IB for additional information.

2.2.2. Cemiplimab Pharmaceutical and Therapeutic Background

Cemiplimab is a fully-human monoclonal antibody targeting the immune checkpoint receptor PD-1 on T-cells. By binding to PD-1, cemiplimab has been shown to block cancer cells from using the PD-1 pathway to suppress T-cell activation.

Anti-PD-1 immunotherapy and chemotherapy combination studies have been conducted in patients with NSCLC. A wealth of clinical data shows that anti-PD-1 monotherapy prolongs progression free survival (PFS) and overall survival (OS) in NSCLC, with the greatest clinical benefit observed in tumors expressing high levels of PD-L1. In addition, clinical data in patients with advanced NSCLC suggest that first line treatment with cemiplimab in combination with chemotherapy, irrespective of PD-L1 expression levels, provides clinically meaningful and statistically significant improvement in OS, PFS, objective response rate (ORR) and duration of response (DOR) vs chemotherapy alone, with a safety profile consistent with cemiplimab monotherapy and platinum-based chemotherapy (Gogishvilli, 2022). Recently, the FDA and the European Commission approved cemiplimab (Libtayo®) for first-line treatment of patients with locally advanced or metastatic, non-small cell lung cancer (NSCLC) whose tumors have ≥50% PD-L1 expression. On November 8, 2022, the Food and Drug Administration approved cemiplimab in combination with platinum-based chemotherapy for adult patients with advanced NSCLC with no EGFR, ALK, or ROS1 aberrations.

Refer to the IB/approved labeling for detailed background information on cemiplimab (REGN2810).

2.3. Benefit/Risk Assessment

This is the first-in-human study of E-602, which is designed to evaluate the safety profile of the drug as a monotherapy and in combination with cemiplimab. Although E-602 has never been administered before to humans, the nonclinical research findings to date have not shown significant toxicities from administration of E-602 to non-human primates. The subjects treated in this study will have advanced cancers with limited or no other treatment options. Subjects will be closely monitored after receiving the study treatment, and dose-modification and discontinuation criteria are prespecified in the protocol. A safety data review committee will meet regularly to review the data and provide oversight in trial conduct and protection of patient safety.

Although E-602 is not expected to significantly stimulate cytokine release in humans based on the preclinical data, precautions are recommended for any drug product that interacts with immune cells to monitor for and manage suspected cytokine or immune-related adverse reactions. This includes frequent assessment of vital signs, blood pressure, and observation for emergent symptoms consistent with cytokine release. Premedication including standard prophylaxis such as antihistamines and acetaminophen are recommended at doses ≥10 mg/kg of E-602 as infusion related reactions have been observed. As of 02-Dec-2022, preliminary data indicate that 12 of 26 treated subjects had infusion related reactions at doses ≥10 mg/kg of E-602 which were primarily ≤Grade 2 and manageable, resolving with concomitant medication and/or slowing of the infusion rate. An isolated Grade 3 infusion related reaction occurred in one subject at the 20 mg/kg E-602 monotherapy dose level which resolved with concomitant medication and did not recur following premedication and slowing of the infusion rate. Two subjects have discontinued study treatment due to ≤Grade 2 recurrent infusion related reactions.

More detailed information about the known and expected benefits, risks, and adverse events (AEs) of E-602 and cemiplimab may be found in the respective IBs.

3. Objectives and Endpoints

Objectives	Endpoints
Dose Escalation Phase (Phase 1)	Епарошіз
Primary	
 To evaluate the safety and tolerability of E-602 as monotherapy in subjects with advanced cancers. To evaluate the safety and tolerability of E-602 in combination with cemiplimab in subjects with advanced cancers. To determine the maximum tolerated dose (MTD) and/or recommended Phase 2 dose (RP2D) of E-602 as monotherapy. To determine the MTD and/or RP2D of E-602 in combination with cemiplimab. 	 Incidence of adverse events (AEs) and serious adverse events (SAEs) graded according to National Cancer Institute (NCI) Common Terminology Criteria for Adverse Events (CTCAE) v5.0. Incidence and nature of dose-limiting toxicities (DLTs) within a modified 3+3 design. The MTD and/or RP2D based on occurrence of DLTs within a modified 3+3 design.
	Noncompartmental DV parameters of E
 To assess the pharmacokinetics (PK) of E-602 as monotherapy. To assess the PK of E-602 in combination with cemiplimab. To evaluate the immunogenicity of E-602 To evaluate preliminary antitumor activity of E-602 as monotherapy in subjects with advanced cancers. To evaluate preliminary antitumor activity of E-602 in combination with cemiplimab in subjects with advanced cancers. 	 Noncompartmental PK parameters of E-602 as monotherapy and in combination with cemiplimab, including the maximum plasma concentration (C_{max}) and area under the plasma concentration-time curve (AUC). Number and percentage of subjects who develop detectable antidrug antibodies (ADA). Objective response rate (ORR) of confirmed complete response (CR) and partial response (PR) using Response Evaluation Criteria in Solid Tumors (RECIST) v1.1 and Immunotherapy Response Evaluation Criteria in Solid Tumors (iRECIST). Duration of response (DOR). Progression-free survival (PFS), defined as the time from the first dose to first evidence of radiographically detectable disease or death from any cause, whichever occurred first. Overall survival (OS).
Dose Expansion Phase (Phase 2)	
Primary	
 To evaluate the preliminary antitumor activity of E-602 as monotherapy in subjects with advanced cancers. To evaluate the preliminary antitumor activity of E-602 in combination with cemiplimab in subjects with advanced cancers. 	 ORR of confirmed CR or PR. DOR of confirmed CR or PR. PFS. OS.

Secondary

- To evaluate the safety and tolerability of E-602 as monotherapy in subjects with advanced cancers.
- To evaluate the safety and tolerability of E-602 in combination with cemiplimab in subjects with advanced cancers.
- To assess the PK of E-602 as monotherapy.
- To assess the PK of E-602 in combination with cemiplimab.
- To evaluate the immunogenicity of E-602

- Incidence of AEs and SAEs graded according to NCI CTCAE v5.0.
- Noncompartmental PK parameters of E-602 as monotherapy and in combination with cemiplimab, including C_{max} and AUC.
- Number and percentage of subjects who develop detectable ADA.

Phase 1 and Phase 2

Exploratory

- To evaluate exploratory pharmacodynamic biomarkers of E-602 activity as monotherapy.
- To evaluate exploratory pharmacodynamic biomarkers of E-602 activity in combination with cemiplimab.
- Immune cell desialylation and activation using FACS
- Immune cell gene expression profiling (RNAseq; Phase 1 E-602 monotherapy only)
- Changes in cytokine levels
- Changes in circulating tumor DNA
- Changes in tumor desialylation by immunohistochemistry (IHC)
- Tumor IHC analysis for immune modulation of different immune cell subtypes
- Tumor gene expression and mutation profiling
- Glycoproteomic profiling
- Genetic variation or single nucleotide polymorphisms (SNPs) in select genes (e.g., glycogenes) (Phase 1 combination and Phase 2 only)

4. Study Design

4.1. Overall Design

This is a Phase 1/2, first-in-human (FIH), open-label, dose escalation and dose expansion study of E-602, administered as a single agent and in combination with cemiplimab, to evaluate the safety, tolerability, PK, pharmacodynamics, and antitumor activity in subjects with advanced cancers.

4.1.1. Study Design Overview

Phase 1: Dose Escalation, Monotherapy and Combination Therapy

Phase 1 of the study consists of 5 planned dose escalation cohorts of E-602 as a monotherapy and 2 planned dose escalation cohorts of E-602 in combination with cemiplimab. Phase 1 monotherapy will treat eligible subjects with melanoma, ovarian cancer, non-small cell lung cancer (NSCLC), colorectal cancer, pancreatic cancer, breast cancer, gastric/EGJ cancer, head and neck cancer, or urothelial cancer. Phase 1 combination with cemiplimab will treat eligible subjects with melanoma, NSCLC, gastric/EGJ cancer, head and neck cancer or urothelial carcinoma. The safety of the dose regimens will be evaluated to identify the maximum tolerated dose (MTD) and recommended Phase 2 dose (RP2D) to be used during Phase 2.

The cohorts of E-602 monotherapy will receive E-602 at the doses of 1, 3, 10, 20 and 30 mg/kg, respectively, via intravenous (IV) infusion once a week. Intermediate dosing cohorts may be added in Phase 1. The first subject dosed in a cohort will be a sentinel subject, with at least 24 hours until any subsequent subjects are dosed in the cohort. No intrasubject dose escalation of E-602 will be permitted.

The cohorts of E-602 in combination with cemiplimab will be initiated at dose level(s) that have previously completed DLT assessments (Cycle 1) as monotherapy. Intermediate dosing cohorts may be added in Phase 1. Subjects in the combination cohorts will receive 20 mg/kg E-602 IV once a week (additional dose levels to be determined) and 350 mg cemiplimab IV once every 3 weeks. The first subject dosed in a cohort will be a sentinel subject, with at least 24 hours until any subsequent subjects are dosed in the cohort. No intrasubject dose escalation of E-602 will be permitted.

Each treatment cycle consists of 21 days. E-602 will be administered on Days 1, 8, and 15 of each cycle. Cemiplimab, if given, will be administered on Day 1 of each cycle. When the cemiplimab combination is administered, cemiplimab should be administered first and E-602 administered at least 30 minutes after the cemiplimab infusion is completed. Subjects receiving ≥10 mg/kg of E-602 as monotherapy or in combination with cemiplimab should receive premedication including antihistamines and acetaminophen as indicated in the Pharmacy Manual. Corticosteroids should be used as premedication for subjects with previous infusion reaction(s) to E-602 as indicated in the Pharmacy Manual (see Pharmacy Manual, Section 10.5).

Dose escalation guidelines for all Phase 1 dose cohorts will utilize a modified 3+3 design. Assessments of DLTs will occur during Cycle 1 (defined as a subject receiving 3 doses of E-602 for monotherapy cohorts and 3 doses of E-602 and 1 dose of cemiplimab for combination therapy cohorts) for all dose cohorts. Safety monitoring for immune-related toxicities will continue for all

subjects for 90 days after treatment discontinuation unless a subsequent cancer therapy is started. All available data will be taken into consideration in selecting the RP2D.

E-602 dose escalation will continue until the MTD is exceeded, unacceptable toxicity is reached, or the RP2D is determined. The Sponsor may terminate dose escalation at an RP2D prior to reaching the MTD based on emerging PK, pharmacodynamic, and safety data.

Any Phase 1 cohort may be backfilled at the judgement of the Sponsor, up to a total of 15 subjects in the dose cohort (dose escalation and backfill) as needed to obtain additional safety, PK, and pharmacodynamic data at a particular dose level.

In addition to DLTs, subjects will be evaluated for safety and tumor response as well as PK and pharmacodynamics, as listed in the Schedule of Activities (SoA) in Section 1.3.

Phase 2: Dose Expansion, Monotherapy and Combination Therapy

Phase 2 consists of dose expansion disease cohorts in subjects with 3 types of advanced tumors: melanoma, NSCLC, and the third type to be determined (ovarian, colorectal, pancreatic, breast, gastric/EGJ, head and neck, or urothelial) based on available data including the Phase 1 results. Phase 2 of the study will employ a 2-stage design, as outlined in Section 9.4. Each disease cohort will be analyzed separately. The E-602 dose(s), i.e., RP2D(s), chosen based on Phase 1 data will be used. E-602 as monotherapy and in combination with cemiplimab will be evaluated separately.

Subjects will be evaluated for safety and tumor response as well as PK and pharmacodynamics, as listed in the Schedule of Activities (SoA) in Section 1.3.

Study Duration and Visit Frequency

- Study duration: approximately 2 years from screening of the first subject to the last visit of the last subject (end of study).
- Treatment duration for individual subjects:
 - o Screening period: up to 4 weeks before Cycle 1 Day 1
 - o Treatment period: up to 1 year from Cycle 1 Day 1 regardless of treatment delays
 - o Follow-up period: up to approximately 15 months from Cycle 1 Day 1
- Visit frequency: approximately up to 7 visits in Cycle 1, up to 5 visits in Cycle 2 and from Cycle 3 onward, approximately weekly visits in each 21-day cycle.

Number of Subjects

The planned total number of subjects to be treated in Phase 1 of the study is up to 87 subjects including up to 42 subjects in dose escalation and 45 subjects in backfilled cohorts. The planned total number of subjects to be treated in Phase 2 of the study is up to 186 subjects.

Total study treatment is up to 273 subjects.

4.1.2. Continued Treatment Beyond Disease Progression

Each subject will receive the study treatment for 1 year, unless the treatment is discontinued for any of the reasons listed in Section 7.1.

Treatment beyond progressive disease (PD) will be allowed as per iRECIST guidelines (Seymour 2017). The following criteria must be met for continued use of the study treatment beyond PD:

- Absence of symptoms and signs indicating clinically significant progression of disease
- No decline in the Eastern Cooperative Oncology Group (ECOG) performance status
- Absence of symptomatic rapid disease progression requiring urgent medical intervention (e.g., symptomatic pleural effusion, spinal cord compression).

At the time of radiographic progression of disease, a subject will be reconsented with emphasis on the FDA-approved therapy and potential clinical benefit that the subject may be foregoing to continue treatment.

4.1.3. Post-treatment Follow-up

For subjects who complete the 1-year treatment, an end-of-treatment (EOT) visit will be conducted, and subjects will return for safety follow-up visits 30 and 90 days after the last dose of study treatment to monitor for safety, including late immune-related toxicities. If prior to completing the 90-day safety follow-up period a subject begins a new cancer treatment, no further safety follow-up is required.

For subjects who discontinue treatment early, an EOT visit will be conducted, and subjects will return for safety follow-up visits 30 and 90 days after the last dose of study treatment. If prior to completing the 90-day safety follow-up period a subject begins a new cancer treatment, no further safety follow-up is required. These subjects will continue to be contacted once every 3 months for disease and survival status through approximately 15 months after the first dose of the study treatment unless the subject has died or withdrawn consent.

4.1.4. Phase 1 Dose-escalation Guidelines

The following modified 3+3 guidelines will be employed on the basis of the number of DLTs observed during Cycle 1 (3 doses of E-602 administered for monotherapy cohorts and 3 doses of E-602 and 1 dose of cemiplimab administered for combination therapy cohorts):

- Each dose level cohort will initially treat 3-6 subjects. At each dose level, at least 3 subjects must be DLT-evaluable prior to dose escalation.
- If 0 subjects experience a DLT, the next cohort will be treated at the next higher dose level.
- If only 1 subject experiences a DLT in 6 DLT-evaluable subjects, the next cohort will be treated at the next higher dose level.
- If 2 or more subjects in any cohort experience a DLT, the MTD will have been exceeded and no further subjects will be treated at this or higher dose levels. Additional subjects will be treated at the next lower dose level if needed to have at least 6 subjects treated at that prior dose level. If at least 6 subjects were previously treated at the prior dose level, that prior dose level will be considered the MTD.

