For subjects who complete the 1-year treatment, an end-of-treatment (EOT) visit will be conducted, and subjects will return for safety follow-up visits 30 and 90 days after the last dose of study treatment to monitor for safety, including late immune-related toxicities. If prior to completing the 90-day safety follow-up period a subject begins a new cancer treatment, no further safety follow-up is required.

For subjects who discontinue treatment early, an EOT visit will be conducted, and subjects will return for safety follow-up visits 30 and 90 days after the last dose of study treatment. If prior to completing the 90-day safety follow-up period a subject begins a new cancer treatment, no further safety follow-up is required. These subjects will continue to be contacted once every 3 months for disease and survival status through approximately 15 months after the first dose of the study treatment unless the subject has died or withdrawn consent.

Phase 1 Dose-escalation Guidelines:

The following modified 3+3 guidelines will be employed on the basis of the number of DLTs observed during Cycle 1 (3 doses of E-602 administered for monotherapy cohorts and 3 doses of E-602 and 1 dose of cemiplimab administered for combination therapy cohorts):

- Each dose level cohort will treat 3-6 subjects. At each dose level, at least 3 subjects must be DLT-evaluable prior to dose escalation.
- If 0 subjects experience a DLT, the next cohort will be treated at the next higher dose level.
- If only 1 subject experiences a DLT in 6 DLT-evaluable subjects, the next cohort will be treated at the next higher dose level.
- If 2 or more subjects in any cohort experience a DLT, the MTD will have been exceeded and no further subjects will be treated at this or higher dose levels. Additional subjects will be treated at the next lower dose level if needed to have at least 6 subjects treated at that prior dose level. If at least 6 subjects were previously treated at the prior dose level, that prior dose level will be considered the MTD.

Dose-Limiting Toxicity (DLT) Definition:

The DLT window of observation for the purposes of dose escalation will be Cycle 1 defined as a subject receiving 3 doses of E-602 for monotherapy cohorts and 3 doses of E-602 and 1 dose of cemiplimab for combination therapy cohorts. Any of the following events will meet the definition of a DLT if assessed by the investigator to be possibly, probably, or definitely related to study treatment:

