7.1.2. Subject Replacement

During Phase 1 dose escalation, subjects who cannot be evaluated for DLT (e.g., discontinued before completing Cycle 1 for reasons other than study treatment-related toxicity) may be replaced. Backfill and Phase 2 subjects will not be replaced.

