9.1. Analysis Sets

DLT Evaluable Set:

Will include all subjects treated in the dose escalation part who have had a DLT within Cycle 1 on study or without a DLT but completed safety assessments through Cycle 1 (3 doses of E-602 administered for monotherapy cohorts and 3 doses of E-602 and 1 dose of cemiplimab administered for combination therapy cohorts). The DLT Evaluable Set will be defined for each dose cohort. Subjects who discontinue prior to completing Cycle 1 (3 doses of E-602 administered for monotherapy cohorts and 3 doses of E-602 and 1 dose of cemiplimab administered for combination therapy cohorts) for reasons other than toxicity may be replaced.

Safety Analysis Set:

Will include all subjects who have received any dose of study treatment. The Safety Analysis Set will be used for safety analyses. Safety Analysis Set may be further defined by the phase of the study, dose, and tumor type.

Efficacy Evaluable Set:

Will include all subjects who receive any dose of study treatment, meet eligibility criteria, have measurable tumor lesions at baseline, and have at least one post-baseline disease assessment per RECIST v1.1. Efficacy Evaluable Set is defined for each cohort in the Phase 2 separately.

Pharmacokinetics (PK) Analysis Set:

Will include all subjects in the Safety Analysis Set for whom adequate data on E-602 plasma concentration are available.

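### Protocol 4.1.4 escalates on DLT-evaluable subjects but confirms the MTD on 6 subjects treated, so the rule, followed literally, can name an MTD on 3 to 5 evaluable subjects; the effect is small

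*Protocol*

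**What the plan says.** Protocol 4.1.4 uses two different counts.

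- **Escalation** is judged on DLT-evaluable subjects. At least 3 must be evaluable at a level. With no DLT the next level opens. With one DLT the condition is "If only 1 subject experiences a DLT in 6 DLT-evaluable subjects".
- **Stopping**: "If 2 or more subjects in any cohort experience a DLT, the MTD will have been exceeded".
- **MTD confirmation** is judged on subjects treated. More subjects are added at the next lower level "if needed to have at least 6 subjects treated at that prior dose level", and then: "If at least 6 subjects were previously treated at the prior dose level, that prior dose level will be considered the MTD". The synopsis has the same wording: "If at least 6 subjects were previously treated at the prior dose level".

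Protocol 9.1 and SAP 3.2 define the DLT-evaluable set. A dose-escalation subject belongs to it after a Cycle 1 DLT, or after completing Cycle 1 without one (3 doses of E-602, plus 1 of cemiplimab in the combination).

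Replacement is permitted, not required. Protocol 7.1.2 covers escalation subjects who cannot be evaluated for DLT and gives as an example those who "discontinued before completing Cycle 1 for reasons other than study treatment-related toxicity) may be replaced". Protocol 9.1 says that subjects leaving before the end of Cycle 1 "for reasons other than toxicity may be replaced", and SAP 3.2 agrees.

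**The concern.** Treated and DLT-evaluable are different sets. A subject who leaves Cycle 1 early without a DLT counts towards the 6 treated but contributes no complete DLT assessment. Take a level that passes with 0 DLTs in 3 and whose next level then stops. Three more subjects are treated at the lower level, and one or more leave Cycle 1 without a DLT. The condition of 6 treated is met with 3, 4 or 5 evaluable subjects, and the text then names that level the MTD.

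The MTD and/or RP2D based on DLTs is a Phase 1 primary endpoint in a first-in-human trial. The 6-subject confirmation exists to add DLT information to a level that may have passed on only 3 subjects. Counting subjects who were not assessed for DLT weakens that purpose.

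**Working it through.** **The plan's own figure.** The documents give no operating characteristics for the MTD rule. The one related figure, up to 42 escalation subjects, reproduces: 5 × 6 + 2 × 6 = 42.

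**What satisfies the literal text.** If 6 were already treated before escalation, the passing results are 0 DLTs in 3, 4, 5 or 6 evaluable, or 1 DLT in 6 evaluable. If the level is topped up afterwards, 1 DLT in 4 or 5 evaluable also meets the wording. With 0 DLTs in 5, a sixth subject could not change the decision, because 1 in 6 passes.

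**Assumptions, none from the documents.** True DLT rate p is 20%, 30% or 40%. Non-evaluability q is 2/26 = 7.7%, 10% or 20%, independent of DLT, with no replacement. The 2/26 treats both stops for infusion reactions in Protocol 2.3 as Cycle 1 stops among the 26 subjects mentioned there. That is only a way to set a scale.

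**Top-up route.**

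1. P(0 DLTs in the first 3) = (1 − p)³.
2. The number evaluable in the top-up is k ~ Bin(3, 1 − q). P(k < 3) = 1 − (1 − q)³ = 21%, 27% and 49% for the three values of q.
3. P(at most 1 DLT in k) is 1 for k = 0 or 1, 1 − p² for k = 2, and (1 − p)³ + 3p(1 − p)² for k = 3. At p = 40% this gives 1, 1, 0.84 and 0.648.
4. P(pass) is step 1 times the average of step 3 over k. At p = 40%, q = 10%: 0.216 × (0.729 × 0.648 + 0.243 × 0.84 + 0.028) = 0.216 × 0.7045 = 0.152. Under a 6-evaluable rule it is 0.216 × 0.648 = 0.140.

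| p | 6 evaluable required | q = 7.7% | q = 10% | q = 20% | only 3 evaluable |
|---|---|---|---|---|---|
| 20% | 45.9% | 46.6% (+0.7) | 46.8% (+0.9) | 47.7% (+1.8) | 51.2% (+5.3) |
| 30% | 26.9% | 27.9% (+1.0) | 28.1% (+1.3) | 29.3% (+2.4) | 34.3% (+7.4) |
| 40% | 14.0% | 14.9% (+0.9) | 15.2% (+1.2) | 16.4% (+2.4) | 21.6% (+7.6) |

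Differences are in percentage points, from unrounded values. The last column needs all three top-up subjects to be non-evaluable, which has probability q³ = 0.05%, 0.1% and 0.8%.

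**Requiring a stop at the next level.** With a true rate there of 50% to 60%, P(stop) = 1 − P(0/3) − P(1/3) × P(0/3) = 0.828 to 0.918. At p = 40% the joint probability is 11.6% to 12.8% under a 6-evaluable rule, 12.6% to 14.0% at q = 10%, and 13.6% to 15.0% at q = 20%.

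**Six treated before escalation.** Exactly 3 of 6 evaluable has probability 20(1 − q)³q³ = 1.5% at q = 10% and 8.2% at q = 20%. Multiplying by 0.216 and 0.828 to 0.918 gives about 0.3% and 1.5% to 1.6%.

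**The case against.** **Treated may mean treated through the DLT window.** Section 4.1.4 opens by tying its rules to DLTs seen in Cycle 1, described by doses given. That reading is sensible as intent, but the bullets do not bear it out. The first bullet itself separates the 3 to 6 subjects treated from the 3 who must be DLT-evaluable.

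**The MTD may never be declared, and the decision rests elsewhere.** The MTD sentence operates only after 2 or more DLTs at a level. Protocol 4.3.1 reports none up to 10 mg/kg. Phase 2 uses the RP2D, chosen on the totality of data (Protocol 4.2), and the Safety Data Review Committee (SDRC) advises on all dosing decisions. This stands and lowers the practical weight. It does not supply the missing number: SAP 7.1 mentions only the 3-subject minimum for committee review.

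**Non-evaluability is already limited.** A delay of more than 14 days due to an AE is itself a DLT if related, so that subject is evaluable, and dosing visits are not to be skipped because of delays. This stands and argues for the lower values of q.

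**The pass probabilities leave out the 1/3-then-1/6 route.** That route already requires 6 DLT-evaluable subjects and is unaffected. Including it at p = 40%, passing goes from 23.3% to 24.5% at q = 10%. The absolute gap is the same and the relative gap is smaller.

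**Stronger readings that the documents do not support.** A reader might infer that subjects who stop for toxicity cannot be replaced. Protocol 9.1 and SAP 3.2 permit replacement for other reasons without excluding this case, and the toxicity wording in 7.1.2 is only an example. A reader might also take "Two subjects have discontinued study treatment due to ≤Grade 2 recurrent infusion related reactions" as proof of Cycle 1 losses, but neither the cycle nor the study part is given.

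**Conclusion.** The mismatch is real. As written, 6 treated can be satisfied with 3 to 5 DLT-evaluable subjects, and no section requires 6 evaluable at the MTD.

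The effect is small: about 0.7 to 1.8 points at a true DLT rate of 20% and 0.9 to 2.4 points at 40%, before requiring that the next level stops. These figures assume 7.7% to 20% non-evaluability, independence from DLT, and a sponsor that replaces nobody. Any replacement shrinks them.

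A reader might take the 5 to 8 point gap as the expected effect. It applies only if just 3 subjects are evaluable, which is rare on the top-up route. The correction is still worth making, because it concerns a primary-endpoint decision in a first-in-human trial and costs little.

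**What to change.** - In Protocol 4.1.4 and the synopsis, replace *treated* with *DLT-evaluable* in the top-up sentence and the MTD sentence. The MTD then needs at least 6 DLT-evaluable subjects with at most 1 DLT.
- In Protocol 7.1.2, Protocol 9.1 and SAP 3.2, state that any non-evaluable escalation or top-up subject will be replaced until 6 are evaluable at the dose to be named the MTD. Include a subject who stops in Cycle 1 for a toxicity that is not a DLT.
- Leave the stopping rule for 2 or more DLTs in any cohort as it is. It is a safety rule, and curing this mismatch does not require changing it.

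The cost is wording and an occasional extra subject. On average 6/0.9 = 6.7 to 6/0.8 = 7.5 subjects are treated to obtain 6 evaluable at 10% to 20% non-evaluability. That exceeds the planned 3 to 6 per escalation cohort but stays within the 15-subject cap.
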